1.1.1 AC699

AC699 is an orally bioavailable ER degrader being investigated for the treatment of patients with locally advanced or metastatic ER+/ human epidermal growth factor receptor 2 negative (HER2-) breast cancer. AC699 is an E3 ligase-engaged chimeric small molecule compound, containing both ligands of human ERα and cereblon (CRBN) E3 ligase.

The pharmacology profile of AC699 has demonstrated that it potently binds to human ER α with an inhibitor constant (K_i) of 0.53 nM and a half-maximal inhibitory concentration (IC50) of 6.02 nM (4.4 ng/mL) and induces rapid ERα degradation in multiple ERα-positive breast cancer cell lines. In *in vitro* studies, ERa degradation was inhibited by epoxomicin (a proteasome inhibitor), which suggests that AC699 degradation of ERα occurs through a ubiquitin-mediated proteasome-dependent mechanism. Functionally, AC699 stopped ERα-regulated transcription in vitro and inhibited the growth of ER-positive cell lines. Cell growth inhibition caused by AC699 was enhanced in the presence of cyclin-dependent kinase (CDK)4/6 inhibitors palbociclib and abemaciclib. The efficacy of oral administration of AC699 against xenografted tumors was demonstrated in 2 studies in mice involving once daily oral administration of 30 to 120 mg/kg of AC699. Once daily oral administration of 30 mg/kg/day (the lowest dose level evaluated) achieved tumor regression in MCF7 xenograft tumors in mice. In a tamoxifen-resistant MCF7 xenograft model, enhanced anti-tumor activity was observed when AC699 was administered in combination with the CDK4/6 inhibitor palbociclib. These in vivo pharmacology studies suggest that AC699 may be able to treat tamoxifen-resistant tumors. Co-administration of AC699 with a CDK4/6 inhibitor shows promise as a therapeutic option for ER-positive breast cancers.

Following repeat oral administration in the GLP-compliant toxicology studies, AC699 exposure in terms of AUC_{0-24h} increased in an approximately dose-dependent manner in both rats and dogs; however, exposure was slightly less than dose proportional across the dose range of 5 to 45 mg/kg/day in dogs following repeat administration. There were no marked sex-based differences in exposure, but in the 28-day toxicity study of AC699 in rats, exposures were 1.4 to 1.9-fold higher in female rats compared to males. In dogs, exposures to AC699 at 45 mg/kg/day decreased in females and slightly decreased in males following repeat dosing. No significant accumulation of AC699 was reported with repeated dosing in both preclinical species.

Following oral administration of AC699 to female rats, the highest exposures were observed in the large and small intestine with limited exposure to the brain. AC699 was quantifiable in mammary gland tissue (*i.e.*, the expected pharmacological site of action) and the ovaries and uterus (2 target tissues observed in toxicology studies). Observed exposures in the evaluated tissues (based on area under the concentration-time curve [AUC]) were greater than that observed in plasma (2,800 ng.h/mL).

AC699 was weakly metabolized by human cytochrome P450 CYP2C8, CYP3A4, and CYP3A5 *in vitro*. AC699 inhibited CYP2B6, CYP2C9, and CYP2C19 by 48.0%, 41.1%, and 39.1% at the highest concentration of 10 μ M, respectively, in the presence of NADPH, with a reported IC₅₀ >10 μ M, without showing time-dependent inhibition. AC699 displayed weak time-dependent inhibition against CYP3A with midazolam as the substrate (31.3% inhibition at a concentration of 10 μ M). AC699 did not directly inhibit CYP1A2, CYP2C8, CYP2D6 or CYP3A at the highest concentration evaluated (10 μ M). AC699 did not significantly induce activity or mRNA expression of CYP2B6, or CYP3A4 *in vitro*, but increased CYP1A2 mRNA

CONFIDENTIAL

Sponsor/Development Innovations Study Numbers: AC699-001/BRE 401

Final Protocol: 07 May 2024 Version 4.0

expression by 1.4- and 3.1-fold in 1 of 3 hepatocyte donors at 0.5 μ M (*i.e.*, 372 ng/mL) and 2 μ M, while no induction of CYP1A2 enzyme activity was observed.

In the 28-day GLP toxicity studies of AC699 in rats and dogs, key organ effects were observed in both species and the effects were considered on target pharmacological effects.

Overall, there were no off-target adverse toxicities observed. In the 28-day oral toxicity study of AC699 in rats, the severely toxic dose in 10% of animals (STD $_{10}$) was considered to be 270 mg/kg/day in females. The 270 mg/kg/day dose level was considered the no-observed-adverse-effect-level (NOAEL) in male rats due to the absence of any adverse findings. In the 28-day oral toxicity study of AC699 in dogs, the highest non-severely-toxic dose (HNSTD) was considered to be 45 mg/kg/day due to the presence of pharmacological effects on the reproductive organs of both sexes.

A human starting dose of 261 mg/day was calculated based on 1/10th the STD₁₀ value in rats from 28-day GLP toxicity studies, and a human starting dose of 250 mg/day was calculated from 1/6th of the HNSTD determined in the 28-day GLP toxicity studies in dogs. However, the proposed starting dose in this clinical study is 100 mg/day which provides an additional 2.5-fold safety margin.

Refer to the Investigator Brochure (IB) for full summaries of preclinical evaluations.

1.1.2 Study Rationale

The ER is a clearly validated oncogenic driver and is expressed in most breast cancers. Fulvestrant, which targets ER, has been approved for the treatment of patients with advanced and metastatic breast cancer. Other SERDs and novel chimeric ER degrader have shown preliminary efficacy in the metastatic setting. This is a first-in-human study of the chimeric ER degrader, AC699.

The dose-escalation portion of this study will begin with 100 mg once daily (QD). Although nonclinical toxicology studies support an AC699 starting dose of up to 250 mg/day, the predicted human efficacious dose range may be as low as 30 mg/day depending on the levels used in human dose projection. Therefore, the initial dose of 100 mg QD was chosen to limit the number of patients exposed to lower efficacious dose levels, while adding an additional 2.5-fold safety margin.

1.2 Potential Risks and Benefits of the Treatment Regimen

The results from the nonclinical pharmacology, pharmacokinetic (PK), and toxicology studies support the clinical development of AC699. The nonclinical toxicology studies of AC699 demonstrated that the drug exerts reversible effects on the female reproductive system that are consistent with the pharmacological mechanism of action of a compound with anti-estrogenic effects. These effects were observed without any other adverse changes. Observed effects on clinical pathology were only observed in 1 species (rats), and were non-adverse, reversible, and are monitorable in clinical studies.

CONFIDENTIAL

Sponsor/Development Innovations Study Numbers: AC699-001/BRE 401

Final Protocol: 07 May 2024 Version 4.0

2. STUDY OBJECTIVES AND ENDPOINTS

Table 1 Study Objectives and Corresponding Endpoints

Primary Objective:	Endpoint/Variable:
Evaluate the safety and tolerability of AC699	Incidence and severity of dose-limiting toxicities (DLTs), treatment-emergent adverse events (TEAEs), and clinically significant Grade 3 or higher laboratory abnormalities
Secondary Objectives:	Endpoint/Variable:
Evaluate the preliminary anti-tumor activity of AC699	Objective response rate (ORR [CR+PR]) as defined by Response Evaluation Criteria in Solid Tumors (RECIST) Version 1.1, clinical benefit rate (CBR) (complete response [CR]+partial response [PR]+stable disease [SD] \geq 24 weeks), duration of response (DOR), disease control rate (DCR), and progression-free survival (PFS)
Characterize the pharmacokinetic (PK) profile of a single dose and after multiple doses of AC699	PK parameters
Exploratory Objectives:	Endpoint/Variable:
Evaluate the pharmacodynamic (PDx) effect of AC699 in ER α degradation	Change of ER α expression in tumors from baseline to post-treatment if tumor tissue is available from paired biopsies
Evaluate the relationship between circulating tumor cells (CTCs) count and administration of AC699	Correlation between CTC count at baseline and post-treatment, and anti-tumor activity (ORR, CBR, DOR, DCR, and PFS)
Evaluate the relationship between estrogen receptor gene 1 (ESR1) mutation status and antitumor activity of AC699	Correlation between ESR1 mutational status and anti-tumor activity (ORR, CBR, DOR, DCR, and PFS)
Evaluate the relationship between circulating tumor DNA (ctDNA) levels and anti-tumor activity of AC699	Correlation between ctDNA levels at baseline & post-treatment and anti-tumor activity (ORR, CBR, DOR, DCR, and PFS)

3. STUDY PATIENT POPULATION AND DISCONTINUATION

3.1 Inclusion Criteria

Patients must meet all the following criteria in order to be included in the research study:

1. Written informed consent, according to local guidelines, signed and dated prior to the performance of any study-specific procedures, sampling, or analyses

CONFIDENTIAL

Study Drug: AC699 Sponsor/Development Innovations Study Numbers: AC699-001/BRE 401

- 2. Adult male and female patients, at least 18 years-of-age at the time of signature of the informed consent form (ICF)
- 3. Female participants must meet one of the following criteria described in a) or b):
 - a) Premenopausal or perimenopausal women must receive concurrent treatment with a luteinizing hormone-releasing hormone (LHRH) agonist beginning at least 4 weeks before the start of trial therapy and agree to continue the LHRH agonist throughout the duration of study treatment, have a negative serum pregnancy test within 7 days of initiating treatment, and agree to follow guidelines for use of highly effective contraception as outlined in Appendix C during the study and for 90 days following the last dose of study drug.
 - b) Postmenopausal women must be defined by as one of the following:
 - i. Age \geq 60, or
 - ii. Spontaneous amenorrhea (i.e., in the absence of chemotherapy, tamoxifen, toremifene, or ovarian suppression) for ≥12 months following cessation of all exogenous hormonal treatment, or
 - iii. 6 months of spontaneous amenorrhea with serum follicle-stimulating (FSH) levels and an estradiol value in the post-menopausal range per institutional standards), or
 - iv. Prior bilateral oophorectomy performed at least 6 weeks before screening, with or without hysterectomy
- 4. Eastern Cooperative Oncology Group (ECOG) Performance Status score of 0 or 1 (Appendix A)
- 5. Patients with a confirmed diagnosis of advanced, unresectable, and/or metastatic breast cancer following disease progression on standard treatment, or for whom no therapy of proven efficacy exists, or who are not amenable to standard therapies
- 6. Patient has a histologically and/or cytologically confirmed diagnosis of estrogen-receptor positive (ER+) breast cancer
- 7. Patient with HER2-negative breast cancer as defined by American Society of Clinical Oncologists/College of American Pathologists (ASCO/CAP) guidelines (Wolff et al. 2018)
- 8. Patients must have received at least 2 prior endocrine regimens in any setting (neoadjuvant, adjuvant or advanced/metastatic) or at least 1 prior line of endocrine therapy if combined with CDK4/6 inhibitor
- 9. Prior chemotherapy is not required, but up to 3 prior regimens of cytotoxic chemotherapy will be allowed in the locally advanced/ metastatic setting
- 10. Patients must have at least 1 measurable lesion according to Response Evaluation Criteria in Solid Tumors (RECIST) Version 1.1 (Appendix B) or at least 1 predominantly lytic bone lesion in the absence of measurable disease
- 11. Acceptable organ function, as evidenced by the following laboratory data:
 - Renal function, as follows:
 - o Creatinine clearance of ≥60 mL/min by the Cockcroft-Gault equation or equivalent

Study Drug: AC699 Sponsor/Development Innovations Study Numbers: AC699-001/BRE 401

- Liver function as follows:
 - Total bilirubin \leq 1.5 × ULN (\leq 5 × ULN for patients with known Gilbert's syndrome)
 - o Aspartate aminotransferase (AST) ≤2.5 × ULN or ≤5 × ULN in the presence of liver metastases
 - o Alanine aminotransferase (ALT) ≤2.5 × ULN or ≤5 × ULN in the presence of liver metastases
- International normalized ratio (INR) ≤2
- 12. Acceptable hematologic function:
 - Hemoglobin ≥9 g/dL
 - Absolute neutrophil count (ANC) ≥1,000 cells/mm³
 - Platelet count \geq 75,000 cells/mm³
- 13. Male patients with female partners of childbearing potential are required to use two forms of acceptable contraception (Appendix C), including one barrier method, during their participation in the study and for 90 days following last dose. Male patients must also refrain from donating sperm during their participation in the study and for 90 days following last dose.
- 14. Life expectancy ≥12 weeks after the start of the treatment according to the Investigator's judgment.
- 15. Backfill patient must have historical testing available to confirm ESR1 mutations and must meet all inclusion criteria listed here.

3.2 Exclusion Criteria

Patients who meet any of the following criteria will be excluded from study entry:

- 1. Treatment with any of the following:
- any cytotoxic chemotherapy, investigational agents or other anti-cancer drugs for the treatment of locally advanced or metastatic breast cancer within 14 days prior to the first administration of AC699
- >3 prior chemotherapy regimens for locally advanced or metastatic breast cancer
- radiation therapy within 14 days prior to first study drug administration that did not resolve to tolerable toxicity, or prior irradiation to >25% of bone marrow. Prior palliative radiotherapy to metastatic lesion(s) is permitted, provided it has been completed 7 days prior to study enrollment and no clinically significant toxicities are expected (e.g., mucositis, esophagitis).
- major surgery within 21 days prior to the first study drug administration (exception: patients may enroll if fully recovered or without intolerable or clinically significant adverse effects but at least 14 days must have elapsed between major surgery and first study drug administration)

CONFIDENTIAL

Sponsor/Development Innovations Study Numbers: AC699-001/BRE 401

Final Protocol: 07 May 2024 Version 4.0

- use of prophylactic growth factors and blood transfusions ≤14 days prior to the first study drug administration
- proton pump inhibitors should not be used within at least 48 hours prior to C1D1 and are prohibited during the study.
- 2. With the exception of alopecia and ≤ Grade 2 peripheral neuropathy, any unresolved toxicities from prior therapy greater than Common Terminology Criteria for Adverse Events (CTCAE) Grade 1 at the time of starting study treatment. Note: Subjects with chronic Grade 2 toxicities that are asymptomatic or adequately managed with stable medication may be eligible with approval by the Medical Monitor and/or Sponsor.
- 3. Known symptomatic brain metastases requiring the use of systemic corticosteroids ≥10 mg/day prednisone or equivalents. Asymptomatic and treated, or asymptomatic untreated brain metastases are allowed as long as patients are clinically stable. Stable doses of anticonvulsants are allowed.
- 4. Any condition that impairs a patient's ability to swallow whole pills. Impairment of gastrointestinal function (GI) or GI disease or other condition at baseline that will interfere significantly with the absorption, distribution, or metabolism of AC699 (e.g., ulcerative disease, uncontrolled nausea, vomiting, diarrhea Grade ≥2, malabsorption syndrome).
- 5. Any of the following cardiac criteria currently or within the last 6 months:
 - mean resting corrected QT interval (QTcF) >470 msec within 28 days prior to the first administration of study drug
 - any clinically important abnormalities (as assessed by the Investigator) in rhythm, conduction, or morphology of resting electrocardiograms (ECGs), e.g., complete left bundle branch block, third-degree heart block
 - congestive heart failure (New York Heart Association Class II-IV [Appendix D])
 - any factors that increase the risk of QTc prolongation or risk of arrhythmic events such as heart failure, acute hypokalemia, congenital long QT syndrome, family history of long QT syndrome or unexplained sudden death under 40 years-of-age, or any new concomitant medication known to prolong the QT interval
 - patients with a left ventricular ejection fraction (LVEF) <50% or the lower limit of normal of the institutional standard within 28 days prior to the first administration of study drug
- 6. As judged by the Investigator, any evidence of severe or uncontrolled systemic diseases, including uncontrolled hypertension, uncontrolled diabetes mellitus, and any serious active infection requiring systemic treatments. Screening for chronic conditions is not required.
- 7. HIV infection with a current or a history of AIDS-defining illness or HIV infection with a CD4+ T cell count <350 cells/μL and an HIV viral load more than 400 copies/μL
- 8. Patients with active viral (any etiology) hepatitis are excluded. However, patients with serologic evidence of chronic HBV infection (defined by a positive hepatitis B surface antigen test and a positive anti-hepatitis core antigen antibody test) who have a viral load below the limit quantification (HBV DNA titer <1000 cps/mL or 200 IU/mL) and are not currently on

Sponsor/Development Innovations Study Numbers: AC699-001/BRE 401

Final Protocol: 07 May 2024 Version 4.0

- viral suppressive therapy may be eligible and should be discussed with the Medical Monitor. Patients with a history of HCV infection who have completed curative antiviral treatment and have a viral load below the limit of quantification may be eligible.
- 9. Diagnosis of other active invasive cancers other than the one treated in this study within 2 years prior to first study drug administration; Exceptions include appropriately treated basal cell or squamous cell skin cancer, or in situ carcinoma of uterine cervix, or other local tumors considered cured by local treatment
- 10. Prior history of allergic reaction to the composition/excipients of AC699
- 11. Psychological, familial, sociological, or geographical conditions that do not permit compliance with the protocol and/or follow-up procedures outlined in the protocol

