- 8. Patients with active viral (any etiology) hepatitis are excluded. However, patients with serologic evidence of chronic HBV infection (defined by a positive hepatitis B surface antigen test and a positive anti-hepatitis core antigen antibody test) who have a viral load below the limit quantification (HBV DNA titer <1000 cps/mL or 200 IU/mL) and are not currently on viral suppressive therapy may be eligible and should be discussed with the Medical Monitor. Patients with a history of HCV infection who have completed curative antiviral treatment and have a viral load below the limit of quantification may be eligible.
- 9. Diagnosis of other active invasive cancers other than the one treated in this study within 2 years prior to first study drug administration; Exceptions include appropriately treated basal cell or squamous cell skin cancer, or in situ carcinoma of uterine cervix, or other local tumors considered cured by local treatment.
- 10. Prior history of allergic reaction to the composition/excipients of AC699.
- 11. Psychological, familial, sociological, or geographical conditions that do not permit compliance with the protocol and/or follow-up procedures outlined in the protocol.

Statistical Methodology:

A 3+3 dose escalation design will be used. Some dose levels may be further expanded to approximately 20 patients to further characterize efficacy, safety, and or PK.

Safety Analysis:

Standard safety assessments will be performed regularly for all patients in the full analysis set (FAS)/safety analysis set (SAS) population during the entire course of the study. Safety will be assessed through the analysis of the reported incidence of treatment-emergent and treatment-related AEs. All AEs will be graded according to NCI CTCAE Version 5.0 and coded using Medical Dictionary for Regulatory Activities (MedDRA) version 25.0 or more recent. In addition, summaries of serious adverse events (SAEs), AEs leading to treatment discontinuation and dose modifications, AEs by maximum NCI CTCAE grade, and AEs related to study treatment will also be collected. Other safety endpoints, including laboratory results will be summarized for all patients in the SAS.

CONFIDENTIAL

Study Drug: AC699 Sponsor/Development Innovations Study Numbers: AC699-001/BRE 401

Efficacy Analysis:

- ORR, defined as the proportion of patients with confirmed CR or PR according to the RECIST Version 1.1 criteria.

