- f Triplicate 12-lead ECGs for safety monitoring will be done at screening, before treatment on Cycle 1 Day 1, Cycle 1 Day 15, and Day 1 of each subsequent cycle, at the EOT, and at any other time the Investigator deems it necessary. ECGs should be assessed before the patient takes the study drug that day, after the patient has rested for at least 3 minutes. ECG assessments should be performed prior to specimen collections or with proper time interval in between as to not artificially alter the vital signs collection. Each recording should be separated by at least 30 seconds. Additional triplicate ECGs will be performed closely before the 1 hour and 4-hour post-dose PK blood sample is collected.
- Triplicate ECGs with PKs (each reading performed at least 30 seconds apart) will be conducted closely before the collection of all pre-dose and 1-hour, 2-hour, 4-hour, and 6-hour post-dose PK blood samples.
- g Echocardiogram (ECHO) at screening and subsequently as clinically indicated. A MUGA scan may obtained in place of ECHO to assess ejection fraction.
- h Review patient menopausal status. Premenopausal or perimenopausal women must receive concurrent treatment with an LHRH agonist and agree to use highly effective contraception as defined in Appendix C. Draw estradiol and FSH levels for participants who do not meet other definitions of postmenopausal as defined in the inclusion criteria, if indicated. A serum pregnancy test is required for all women of childbearing potential (WOCBP). It is not required for postmenopausal women. Pregnant women are not eligible for this study.
- ⁱ HIV, HBV, HCV testing see exclusion criteria in Section 3.2.
- ^j SAEs are required to be followed-up until resolution or the SAE stabilizes
- Pharmacokinetic (PK) sampling will be done during Cycles 1, 2, 3, 4, and 6. The visit days and sampling time points as outlined in Appendix F are to be followed (Cycle 1 Day 1 and Cycle 1 Day 15 PK samples will be collected at pre-dose; at 1, 2, and 4 h ours post-dose [± 5 min]; 6 and 8 hours post-dose [± 10 min]; and 24 hours post dose [± 1 hour]). On Cycle 2 Day 1, Cycle 3 Day 1, Cycle 4 Day 1, and Cycle 6 Day 1, a pre-dose PK sample will be collected from all patients.) Additional PK samples may be required for safety reasons or if a patient requires a modification to their dose of AC699.

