A cumulative incidence of any of the following treatment-related events will trigger a hold on further patient enrollment for all dose cohorts until the SRC determines if it is safe to continue:

- Grade 4 adverse events (AEs) > 25%,
- Serious adverse events (SAEs) > 25%,
- AEs leading to discontinuation from study > 25%,
- Grade 5 AEs > 10%.

The 3+3 dose-escalation procedure is shown in Table 2.

CONFIDENTIAL

Study Drug: AC699 Sponsor/Development Innovations Study Numbers: AC699-001/BRE 401

Table 2 Dose-Escalation (3+3) Design

Number of Patients with a DLT	Action
0 of 3 patients	Escalate to next dose level
1 of 3 patients	Accrue additional evaluable patients at the current dose level (for a total of up to 6 evaluable patients) ^a
1 of 6 patients	Escalate to the next dose level
2 or more patients in a dose level group of up to 6 patients	The MTD has been exceeded

DLT = dose-limiting toxicity, MTD = maximum-tolerated dose

Dose-Limiting Toxicity

Toxicity will be assessed using the NCI CTCAE Version 5.0 unless otherwise specified. Dose-limiting toxicities thought to be related to AC699 during the DLT period (first 28 days) will be defined as any of the following toxicities if considered at least possibly related to study treatment, i.e., not attributable to the disease or disease-related process under investigation, or other non-study related explanation, and that means at least 1 of the hematologic or non-hematologic criteria below:

Dose-limiting toxicities (DLTs) will be defined as follows:

• Any Grade 5 toxicity

Hematological:

- o Grade 4 neutropenia for >7 days; or febrile neutropenia (ANC <1000/mm³ with a single temperature of >38.3° C [101° F] or a sustained temperature of ≥ 38° C [100.4° F] for more than 1 hour)
- o Grade 4 thrombocytopenia; or Grade 3 thrombocytopenia associated with clinically significant bleeding, including any bleeding that warrants a platelet transfusion
- o Grade 4 anemia (life-threatening consequences requiring urgent interventions)

• Non-hematological:

- o Grade 3 or 4 non-hematologic toxicity, with the **exception of**:
 - Alopecia;
 - Grade 3 nausea, vomiting, or diarrhea if well-controlled by supportive care within 72 hours;
 - Grade 3 skin rash that improves in ≤7 days, with or without supportive care;
 - Grade 3 fatigue that improves in ≤ 7 days, with or without supportive care;
 - Grade 3 endocrinopathies that only require treatment with hormone replacement therapy;

CONFIDENTIAL

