Sponsor/Development Innovations Study Numbers: AC699-001/BRE 401

Final Protocol: 07 May 2024 Version 4.0

^a For a patient to be considered "evaluable," he or she must have met the minimum safety evaluation requirements of the study, and/or experienced a DLT.

- Grade 3 non-hematologic laboratory abnormalities, other than liver function tests, will not be considered a DLT unless they are associated with clinical manifestations which lead to medical intervention and/or hospitalization
- Potential drug-induced livery injury consistent with Hy's Law (Appendix E),
 defined as AST and/or ALT > 3 × ULN with concurrent total bilirubin > 2 × ULN
 without findings of cholestasis (alkaline phosphatase [ALP] >2 × ULN)
- Grade 3 or higher electrolyte abnormality that lasts > 72 hours, unless the patient
 has clinical symptoms, in which case all Grade 3 or higher electrolyte abnormality
 regardless of duration should count as a DLT

Determination of Dose-Limiting Toxicities

The patient population used for determination of DLTs will consist of patients who have met the minimum safety evaluation requirements of the study, and/or who have experienced a DLT. Minimum safety evaluation requirements will be met if, during Cycle 1 of treatment, the patient receives at least 75% of planned total doses of AC699, completes all required safety evaluations, and is observed for at least 28 days following the first dose of AC699. Patients who have experienced a DLT may be allowed to continue treatment at a lowered dose, if in the opinion of the Investigator, Medical Monitor, and Sponsor, they continue to derive benefit.

Patients who discontinue treatment early due to disease progression or withdrawal will be asked to have all EOT safety evaluations performed as described in the protocol (see Section 7.6). If a patient withdraws from treatment during Cycle 1 due to any reason other than DLT and does not meet the minimum requirements for DLT assessment, that patient will be replaced.

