7.2 Screening

At enrollment, each potential research patient will provide written informed consent ≤28 days prior to first dose of study drug administration and prior to starting any study-specific procedures. Upon signature of the ICF, patients will be assigned a unique subject number as enrollment (screening) occurs.

The screening assessments described in the Schedule of Assessments will be collected, reviewed, and determined to be acceptable by the site Principal Investigator or designee after obtaining informed consent prior to the first dose of study drug administration. Patients who do not meet all inclusion criteria, or who meet an exclusion criterion, may be rescreened once. Rescreening is at the discretion of the Investigator and the reason for rescreening should be discussed with the Sponsor. The Sponsor or designee will review results from the screening visit prior to enrollment to confirm patient selection for the study.

The following screening parameters should be recorded ≤28 days prior to first dose of study drug administration:

- ECHO (This test may be repeated as clinically indicated.) A MUGA scan maybe obtained in place of an ECHO to determine ejection fraction.
- Pre-treatment biopsy (optional)
- Tumor (radiographic) assessments
- Review patient menopausal status. Premenopausal or perimenopausal women must receive concurrent treatment with LHRH agonist and agree to use highly effective contraception as defined in Appendix C. Draw estradiol and FSH levels for participants who do not meet other definitions of postmenopausal as defined in the inclusion criteria, if indicated.
- HIV, HBV, and HCV testing

The following screening parameters should be recorded ≤7 days prior to first dose of study drug administration:

- Medical history and demographics
- Physical examination
- ECOG performance status
- Vital signs (including height and weight)
- Triplicate ECGs. The screening ECG should be assessed before other procedures and after the patient has rested for at least 3 minutes. Each recording should be separated by at least 30 seconds.

CONFIDENTIAL

Sponsor/Development Innovations Study Numbers: AC699-001/BRE 401

Final Protocol: 07 May 2024 Version 4.0

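### Exclusion 7 prints the HIV viral-load cut-off per µL (400 copies/µL = 400,000 copies/mL), probably a unit carried over from the CD4 count; the sponsor should confirm it and state it per mL (minor)

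*Protocol*

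**What the plan says.** Exclusion 7 has two limbs. The first excludes HIV infection with an AIDS-defining illness, current or past. The second excludes HIV infection when two laboratory conditions hold together: a CD4 count below 350 cells/µL "and an HIV viral load more than 400 copies". Section 3.2 prints the unit as per µL: "HIV viral load more than 400 copies/μL". The Synopsis prints the same number and the same unit.

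The next criterion, exclusion 8, contains the only other numeric viral load in the eligibility lists. In both the Synopsis and Section 3.2 it is per mL: "HBV DNA titer <1000 cps/mL or 200 IU/mL". Exclusion 8 admits certain patients with chronic HBV, and patients with treated HCV, only when their viral load is below the limit of quantification.

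No other part of the protocol gives an HIV threshold. Footnote i of the Schedule of Assessments only points back: "HIV, HBV, HCV testing see exclusion criteria in Section 3.2". The wording in Section 3.2 is therefore the rule that sites will apply.

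Two other provisions bear on the same patients. Exclusion 6 leaves it to the Investigator to exclude severe or uncontrolled systemic illness, including "any serious active infection requiring systemic treatments". Section 7.2 adds a check before enrollment: "The Sponsor or designee will review results from the screening visit prior to enrollment to confirm patient selection for the study".

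**The concern.** The CD4 count is naturally per µL. The viral load that follows it in the same sentence carries the same denominator, while the viral load in the next criterion is per mL. That pattern suggests a unit copied across.

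The unit matters because the CD4 and viral-load conditions are joined by a conjunction. If the viral-load condition acts only at very high values, the whole second limb acts only there. A patient with marked immunodeficiency and substantial viremia, but no AIDS-defining illness so far, would then pass criterion 7 and could be considered for a first-in-human drug. If the limit was meant per mL, the same patient is excluded. At stake are who is eligible, the safety of a small group of patients, and whether sites decide such cases in the same way.

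**Working it through.** **Inputs.** CD4 cut-off: below 350 cells/µL (exclusion 7). HIV viral-load cut-off: more than 400, unit copies/µL (exclusion 7, Synopsis and Section 3.2). Conversion: 1 mL = 1000 µL.

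**Step 1: the printed limit on the per-mL scale.**
400 copies/µL × 1000 µL/mL = 400,000 copies/mL.

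**Step 2: distance between the two readings.**
400,000 / 400 = 1000, or 3.0 on the log10 scale. The value of 400 copies/mL is an assumption about intent; the documents do not state it.

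**Step 3: criterion 7 under each reading, for HIV infection without an AIDS-defining illness.**

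| CD4 (cells/µL) | Viral load (copies/mL) | As printed (per µL) | If per mL was meant |
|---|---|---|---|
| below 350 | up to 400 | not excluded | not excluded |
| below 350 | above 400, up to 400,000 | **not excluded** | **excluded** |
| below 350 | above 400,000 | excluded | excluded |
| 350 or more | any | not excluded | not excluded |

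Only the second row depends on the unit. An AIDS-defining illness excludes the patient on either reading.

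**Step 4: an example in the affected row.** CD4 100 cells/µL and 300,000 copies/mL. 300,000 / 1000 = 300 copies/µL, which is not more than 400, so criterion 7 as printed does not exclude the patient. On the per-mL reading, 300,000 is more than 400 and the patient is excluded.

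**Step 5: which unit is likelier, from the documents alone.**
- For a slip: the CD4 count in the same sentence is per µL; the HBV load in the next criterion is per mL; and the HBV and HCV exceptions there require virus below quantification, a pattern that a limit of 400,000 copies/mL does not fit. These are different viruses, so this supports the inference without settling it.
- Against: the two copies of exclusion 7 agree, and the summary of changes in Appendix G records edits to exclusions 1, 5 and 6 but none to 7. Agreement is also what copying one error would produce.
- A PDF reading fault is unlikely, because the unit appears with the viral load in two separate places.

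**Step 6: effect on the analysis.** The SAP's only stated use of the HIV result is a baseline summary (SAP Section 4.2.2), and the SAP tests no hypothesis (SAP Section 2.4). No sample size, endpoint or analysis rule is derived from the cut-off.

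**The case against.** The strongest reply is that the error is inferred. The unit is explicit and is the same in both places, there is no second HIV figure to contradict it, and the supporting comparison is with another virus. This stands: the documents support a query, not a finding of error. A reader might infer that 400 copies/mL is established as the intended limit. It is not.

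The second reply is that the gap is narrower than the table suggests. A patient with CD4 100 cells/µL and 300,000 copies/mL is a natural candidate for exclusion 6, Sponsor review precedes enrollment, and inclusion 14 requires a life expectancy of at least 12 weeks. This stands in part. These checks are real, but none states an HIV threshold. Someone consulting criterion 7 for guidance would find that it does not exclude the patient, so decisions could differ between sites.

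The third reply is that few patients, perhaps none, are affected. The documents give no HIV prevalence or viral-load distribution, so the number cannot be estimated and none is offered here. That is why the point is minor. It does not remove the reason to clarify a safety-related limit that is open to a 1000-fold difference in reading.

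**Conclusion.** The point holds as a minor eligibility and patient-safety correction. As printed, the limit is 400,000 copies/mL. Criterion 7 then leaves in patients with CD4 below 350 cells/µL, no AIDS-defining illness and a viral load above 400 and up to 400,000 copies/mL. The arithmetic is certain. That the unit was carried over from the CD4 count is probable and rests on the internal comparison only, so confidence in the slip is medium.

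A reader might go further and infer that the cut-off distorts the trial's results through DLTs or time-to-event endpoints. The documents do not support that. A DLT must be at least possibly related to AC699 and not due to the disease "or other non-study related explanation", and the enrollment-hold rules count treatment-related events. A patient who leaves treatment in Cycle 1 for a reason other than a DLT and "does not meet the minimum requirements for DLT assessment, that patient will be replaced"; replacement takes the place of a patient who is not evaluable, so it is not a route into the DLT count. Nor does every death become a PFS event, since SAP Table 4 censors deaths after two or more missed tumor assessments. An unrelated adverse event would be tabulated as it would for any patient, but nothing in the documents allows that to be sized. No planned analysis needs to change.

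**What to change.** Ask the sponsor to confirm the intended cut-off, then edit exclusion 7 in the Synopsis and in Section 3.2.

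- If 400 copies/mL was meant, change copies/µL to copies/mL for the HIV viral load in both places.
- If 400 copies/µL was meant, keep the value but print it as 400,000 copies/mL in both places, so that it is explicit and on the same scale as the HBV limit.

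Leave the CD4 cut-off, its per-µL unit and the conjunction as they are; nothing in the documents speaks against them.

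The cost is one query and a two-place text edit at the next amendment. If the unit becomes per mL, eligibility is slightly stricter for viremic patients with CD4 below 350 cells/µL.
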